11.6. Stopping rules

Not applicable

11.7. The Level of Statistical Significance

The level of statistical significance will be set at $p < 0.05$.

11.8. Procedure for Accounting for Missing, Unused, and Spurious Data.

For multivariate models, we will impute missing covariates using fully conditional specification implemented using the Multivariate Imputation by Chained Equations (MICE) algorithm (17). The multiple imputation model will include all covariates, alongside the relevant outcome.

11.9. Procedures for Reporting any Deviation(s) from the Original Statistical Plan

Any deviation from the statistical analysis plan will be described and justified in all study publications.

12. DATA MANAGEMENT

The plan for the data management of the study are outlined below. There is not a separate Data Management document in use for the study.

12.1. Source Data

This study requires accessing and linking confidential health care records. Access to these data will be subject to approval from a REC and Section 251 support from the CAG.

Data linkage

Eligible participants will be identified by ICNARC from the CMP audit. Each eligible participant will be assigned a pseudonymous “study key”. The study key will be sent to the other participating organisations for linkage alongside the following direct identifiers:

- Date of birth
- NHS number
- Postcode
- Sex/gender

Linkage will be performed by each participating organisation, following the principles of the NHS Digital matching algorithm, after which all direct identifiers will be removed. Only pseudonymised data (including the study key) will be securely transferred to the Sponsor (Critical Care Research Group, University of

Oxford), where researchers will assemble these data sources for analysis. At no point will direct identifiers be sent to the Sponsor.

Data sources

The following data sources will be linked to the CMP audit:

- NHS Digital
 - Hospital Episode Statistics (HES)
 - Admitted Patient Care
 - Outpatients
 - Maternity Services Data Set (MSDS)
 - Civil Registration (deaths)
 - Emergency Care Data Set (ECDS)
 - Hospital Episode Statistics Accident and Emergency
 - GPES Data for Pandemic Planning and Research (COVID-19)
- Patient Episode Database for Wales (PEDW)
- UK Renal Registry (UKRR)
- National Institute for Cardiovascular Outcomes Research (NICOR)
- Stroke Sentinel National Audit Programme (SSNAP)

The study will also link data from the UK Obstetric Surveillance System (UKOSS) to identify patients who were pregnant at the time of ICU admission. As UKOSS does not collect direct identifiers, it will be linked to the pseudonymous data set using probabilistic matching.

Data timeframes

On a per patient level, the study will request 5 years of diagnostic coding data prior to ICU admission (to accurately assess prior medical co-morbidities) and 1 year post hospital discharge (to assess the outcomes of this study). The use of a 5 year window of prior diagnostic coding data is based on previous literature that has shown this enhances data accuracy (14). This is preferable to relying solely on the diagnostic coding relating to the hospital admission, as complications cannot be differentiated from prior co-morbidities (15).

Data storage for analysis

The Sponsor will hold pseudonymised data within a secure “Data Safe Haven”, which is owned and maintained by the group. The “Data Safe Haven” is a computing environment which has been designed to store and analyse large datasets in a manner that is safe and secure. It conforms to NHS Digital Security Toolkit and Cyber Essentials Plus accreditation. The environment is designed to prevent patient level data leaving this environment.

ICNARC will hold data within a secure environment, which conforms to the NHS Digital Security Toolkit.

12.2. Access to Data

The final pseudonymised dataset will be accessed by authorised members of the study team at the University of Oxford and ICNARC for analysis purposes. At the University of Oxford, access will be via the Data Safe Haven subject to compliance with local information governance policies. Pseudonymised data will also be securely transferred to ICNARC and accessed via secure servers managed by ICNARC.

12.3. Data Recording and Record Keeping

All study records will be electronic -- their generation is detailed above. All records will be subject to quality assurance policies both at the University and research group level. These are designed to guarantee the accuracy and validity of the study data.

The participants will be identified by a unique study number (pseudonymous study key).

13. QUALITY ASSURANCE PROCEDURES

All research team members will be trained in Information Governance, data protection and confidentiality. The study may be monitored, or audited in accordance with the current approved protocol, GCP, relevant regulations and standard operating procedures.

13.1. Risk assessment

This is a retrospective observational study, where researchers will not interact directly with patients or intervene in their care.

This study requires access to confidential patient records. Eligible patient records will be identified by ICNARC from the CMP audit and linked with follow-up data held by NHS Digital and three national audit projects. Directly identifiable data is only required for record linkage and will not be available to the Sponsor.

To mitigate the risk of reidentification of participants and the risk of data loss we will undertake the following:

- All records will be accessed and de-identified at each participating site, using a dedicated computer that will conform to NHS information security standards.
- Only pseudonymous personal data will be transferred via secure/encrypted protocols to the coordinating centre (Critical Care Research Group (CCRG), Nuffield Department of Clinical Neurosciences, Oxford University).
- Only pseudonymous personal data will be held by the CCRG.
- Pseudonymous personal data will be held inside the Sponsors "Data Safe Haven" which conforms to the same NHS standards of information security and cyber security.

13.2. Study monitoring

All research team members will be fully trained in Information Governance, data protection and confidentiality. The study may be monitored, or audited in accordance with the current approved protocol, GCP, relevant regulations and standard operating procedures.

13.3. Study Committees

Study management group

The study management group will consist of the chief investigator and the named investigators listed under Key Contacts. The study management group will be primarily responsible for the running and conduct of the study. They will be responsible for ensuring that standard operating procedures are followed and that regulations are adhered to. Where appropriate public patient involvement will be gained in any changes or amendments that are needed during the study.

14. PROTOCOL DEVIATIONS

Any deviations from the protocol will be documented in a protocol deviation form and filed in the study master file.

15. SERIOUS BREACHES

A “serious breach” is a breach of the protocol or of the conditions or principles of Good Clinical Practice which is likely to affect to a significant degree –

- (a) the safety or physical or mental integrity of the trial subjects; or
- (b) the scientific value of the research.

In the event that a serious breach is suspected the Sponsor must be contacted within 1 working day. In collaboration with the C.I., the serious breach will be reviewed by the Sponsor and, if appropriate, the Sponsor will report it to the approving REC committee and the relevant NHS host organisation within seven calendar days.

16. ETHICAL AND REGULATORY CONSIDERATIONS

16.1. Declaration of Helsinki

The Investigator will ensure that this study is conducted in accordance with the principles of the Declaration of Helsinki.

16.2. Guidelines for Good Clinical Practice

The Investigator will ensure that this study is conducted in accordance with relevant regulations and with Good Clinical Practice.

16.3. Approvals

Following Sponsor approval, the protocol, and any Privacy notification material will be submitted to an appropriate Research Ethics Committee (REC), CAG and HRA (where required) and host institutions for written approval.

The Investigator will submit and, where necessary, obtain approval from the above parties for all substantial amendments to the original approved documents.

16.4. Other Ethical Considerations

16.5. Reporting

The CI shall submit once a year throughout the study, or on request, an Annual Progress report to the REC Committee, CAG, HRA (where required) host organisation, Sponsor and funder (where required). In addition, an End of Study notification and final report will be submitted to the same parties.

16.6. Transparency in Research

We will register the study on ClinicalTrials.gov.

16.7. Participant Confidentiality

The study will comply with the General Data Protection Regulation (GDPR) and Data Protection Act 2018, which require data to be de-identified as soon as it is practical to do so. The processing of the personal data of participants will be minimised by making use of a unique participant study number only on all study documents and any electronic database(s). All documents will be stored securely and only accessible by study staff and authorised personnel. The study staff will safeguard the privacy of participants' personal data.

16.8. Expenses and Benefits

No payments or any other benefits will be provided to participants.

17. FINANCE AND INSURANCE

17.1. Funding

The study is funded by the University of Oxford's COVID-19 Research Response Fund (Ref: 0009471).

17.2. Insurance

The University has a specialist insurance policy in place which would operate in the event of any participant suffering harm as a result of their involvement in the research (Newline Underwriting Management Ltd, at Lloyd's of London).

17.3. Contractual arrangements

Appropriate contractual arrangements will be put in place with all third parties.

18. PUBLICATION POLICY

The Investigators will be involved in reviewing drafts of the manuscripts, abstracts, press releases and any other publications arising from the study. Authors will acknowledge that the study was funded by the University of Oxford's COVID-19 Research Response Fund (Ref: 0009471). Authorship will be determined in accordance with the ICMJE guidelines and other contributors will be acknowledged.

19. DEVELOPMENT OF A NEW PRODUCT/ PROCESS OR THE GENERATION OF INTELLECTUAL PROPERTY

Ownership of IP generated by employees of the University vests in the University. The University will ensure appropriate arrangements are in place as regards any new IP arising from the study.

19. ARCHIVING

The final linked anonymised study dataset will be stored securely within the CCRG data safe haven and ICNARC servers. Ethical approval will be sought for ongoing storage of study data as a research database. Study data will be available for future research/analysis and access will be governed by the Critical Care Research Group (CCRG) Data Access Committee (DAC). Any additional analyses will be restricted to the overall purpose of better understanding the epidemiology of and outcomes from, critical illness. All outputs will be restricted to aggregate data with small numbers suppressed in line with the HES analysis guide.

21. APPENDIX A: DATA FLOW DIAGRAM

Please see attached Data Flow Diagram

22. APPENDIX C: AMENDMENT HISTORY

Amendment No.	Protocol Version No.	Date issued	Author(s) of changes	Details of Changes made
1	V3	02/08/2021	[name], [name], [name]	
 • Added 5 years of prior data for co-morbidity assessment (7.3) • Updated wording around data sources and the section this applies to (7.3, 12.1)
2	V4	02/12/2021	[name], [name]	
 • Study end date changed to 31st July 2022
3	V5	17/06/2022	[name] and study team	
 • Study end date changed to 31st July 2023. Study length updated accordingly

List details of all protocol amendments here whenever a new version of the protocol is produced.

Protocol amendments must be submitted to the Sponsor for approval prior to submission to the REC committee and HRA (where required).

Outcomes of Patients who survived Treatment on an Intensive Care unit for COVID-19 in England and Wales: a comparative retrospective cohort study

1. Introduction

1.1. Background and rationale

1.1.1. Background

The severe acute respiratory syndrome coronavirus 2 (SARS-CoV-2) emerged in late 2019. By mid-July 2020 14 million people globally had been infected, of which over 600,000 died of coronavirus disease 2019 (COVID-19) (1). In the UK, nearly 20% of patients hospitalised with COVID-19 were transferred to an intensive care unit (ICU) or high dependency ward (2). In total, over 10,000 patients have been treated for COVID-19 on an ICU in England and Wales. On average, 50% of these patients survived to hospital discharge, although survival rates appeared to increase over this period (3,4). The long-term impact on the health of survivors is unknown.

Previous studies have shown that critically ill patients who survive ICU treatment are at greater risk of death and report lower health-related quality of life when compared with population norms (5–7). While pre-existing comorbidities partially account for these differences, organ damage caused by critical illness and the impact of intensive organ support given in the ICU likely also play a role (8). Analysis by the Intensive Care National Audit and Research Centre (ICNARC) suggests that patients admitted with COVID-19 receive higher intensity organ support and suffer more complications than observed in other viral respiratory infections (4). For example, nearly all COVID-19 patients required respiratory support, with nearly 60% receiving mechanical ventilation (compared to 43% with viral pneumonias) (4). Around one third of patients also required advanced cardiovascular or renal support (4,9). Cardiac (myocarditis, heart failure, arrhythmias, acute coronary syndrome) and venous thrombotic complications (e.g. pulmonary embolism) were not uncommon (10–12). Although rare, some patients developed neurological complications such as stroke, encephalitis and Guillain-Barré syndrome (13).

1.1.2. Aim

This statistical analysis plan describes a retrospective cohort study aiming to characterise outcomes for patients treated on an ICU with COVID-19 in England and Wales, one year after discharge from hospital. The study will use existing national audit data linked to routine healthcare datasets.

2.1. General study design and plan

This is a retrospective cohort study of outcomes for patients treated on an ICU in England and Wales, one year after discharge from hospital. Our primary group will include patients admitted to ICU with confirmed COVID-19 between 1st January and 1st July 2020, who were discharged alive from hospital. We will use the ICNARC Case Mix Programme (CMP) to identify comparator groups of emergency ICU admissions, to which outcomes in the primary group can be compared. Once identified, each cohort will be linked to the national data sets to obtain information on subsequent hospitalisations, and longer-term mortality, cardiac and renal outcomes.

The study will be reported using the REporting of studies Conducted using Observational Routinelycollected health Data (RECORD) (14).

2.2. Sample size, power, and detectable difference

The study size will be determined by the number of ICU survivors available from the CMP. The CMP currently holds around 10,000 patients admitted with confirmed COVID-19 between January and July 2020, of which ≈5,000 survived to hospital discharge. Of the survivors, we expected 90% (4,600) to have been admitted to an ICU in England or Wales.

Prior to the COVID-19 pandemic, there were around 130,000 emergency ICU admissions per annum in the CMP. Of these, around 100,000 survived to hospital discharge. We expect ≈90,000 to have been admitted to an ICU in England or Wales.

Study participants will include around 3.5 years of pre-pandemic admissions (90,000 x 3.5 = 315,000) and 4,600 COVID admission during the pandemic giving a total sample size of 319,600.

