8. PARTICIPANT IDENTIFICATION

8.1. Study Participants

8.2. Inclusion Criteria

- Age ≥ 16 years
- Admitted to an adult, general ICU in England or Wales as an emergency (unplanned)
- Admitted to ICU for either:
 - confirmed COVID-19 between 1st January to 1st July 2020
 - without confirmed COVID-19 between 1st July 2016 and 1st July 2020

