11.3. Sample Size Determination

The study size will be determined by the number of ICU survivors available from the CMP. The CMP currently holds around 10,000 patients admitted with confirmed COVID-19, of which ≈5,000 survived to hospital discharge. Of the survivors, we expected 90% (4,600) to have been admitted to an ICU in England or Wales.

Prior to the COVID-19 pandemic, there were around 130,000 emergency ICU admissions per annum in the CMP. Of these, around 100,000 survived to hospital discharge. We expect ≈90,000 to have been admitted to an ICU in England or Wales.

Study participants will include around 3.5 years of pre-pandemic admissions ($90,000 \times 3.5 = 315,000$) and 4,600 COVID admission during the pandemic giving a total sample size of 319,600.

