11.4. Analysis populations

Primary group

Our primary group will be patients admitted with confirmed COVID-19 between 1st January to 1st July 2020.

Comparator groups

The primary comparator group will be patients admitted to ICU with viral or bacterial pneumonia between 1st July 2016 and 1st July 2019.

Secondary comparator groups will include:

- All emergency ICU admissions between 1st July 2016 and 1st July 2019
- All emergency ICU admissions between 1st July 2016 and 1st January 2020 where the primary diagnosis was not COVID-19
- All emergency ICU admissions between 1st January and 1st July 2020 where the primary diagnosis was not COVID-19

Pregnant patients

We will undertake a sub-group analysis in patients who were pregnant when treated for COVID-19 on ICU between 1st January and 1st July 2020.

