4.4.4. Non-COVID ICU admissions 1st January 2020 – 1st July 2020

All emergency ICU admissions between 1st January 2020 and 1st July 2020 where the primary diagnosis was not COVID-19. This cohort includes patients admitted to ICU concurrently to the primary COVID-19 cohort. While this cohort will likely be small, it will possibly provide a fairer comparison of outcomes if the pandemic did affect the healthcare provision during follow-up (i.e. if there were a reduction in the number of hospital admissions for non-Covid causes during the period of the pandemic due to restrictions).

5. Analysis

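### Does the declared total of 319,600 need correcting because it leaves out the non-COVID admissions of January to July 2020?

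*SAP*

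**What the plan says.** Both documents start from availability rather than from a power target. SAP 2.2 puts it this way: "The study size will be determined by the number of ICU survivors available from the CMP". It then takes about 90,000 emergency survivors a year in England and Wales and sets out the sum: "Study participants will include around 3.5 years of pre-pandemic admissions (90,000 x 3.5 = 315,000) and 4,600 COVID admission during the pandemic". The SAP calls the result, 319,600, the total. Protocol 11.3 has the same two terms and the same result: "and 4,600 COVID admission during the pandemic giving a total sample size of 319,600". The synopsis (protocol section 3) gives 319,600 with no breakdown.

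The eligibility window is longer than the period counted. Protocol 8.2 and SAP 4.1.1 both admit patients "without confirmed COVID-19 between 1st July 2016 and 1st July 2020". Protocol 11.4 lists among its secondary comparators "All emergency ICU admissions between 1st January and 1st July 2020 where the primary diagnosis was not COVID-19". SAP 4.4.4 defines the same cohort and comments on its size and use: "While this cohort will likely be small, it will possibly provide a fairer comparison of outcomes". Neither document gives a number for it.

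**The concern.** A figure presented as the total should match the population that the criteria define. Here the non-COVID window runs for 4.0 years and the sum covers 3.5. The missing half-year is not a leftover: it is a separate comparator cohort, which the SAP values because those patients were followed up under the same pandemic conditions as the COVID-19 group. The exploratory comparison with other respiratory infections in the same months draws on it too.

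If the total were an input to anything, leaving out a cohort would carry through to it. Three things could be at stake: a power or precision claim resting on the wrong number, doubt over whether these patients are in the study at all, and a published count that differs from the declared one for a reason the plan never gave. The synopsis is the most exposed place, because a reader there sees the number without its parts.

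**Working it through.** **Inputs.** About 90,000 survivors a year, 3.5 years and 4,600 COVID-19 survivors (SAP 2.2, protocol 11.3); non-COVID window 1 July 2016 to 1 July 2020 (protocol 8.2, SAP 4.1.1); uncounted cohort 1 January to 1 July 2020 (protocol 11.4, SAP 4.4.4).

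**1. The plan's own figure.** 90,000 × 3.5 = 315,000, and 315,000 + 4,600 = 319,600. It reproduces exactly. The two terms use up the whole total, so the 2020 non-COVID cohort contributes zero.

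**2. The time left out.** 1 July 2016 to 1 January 2020 is 1,279 days (3.5 years). To 1 July 2020 it is 1,461 days (4.0 years). The difference is 182 days, and 182 / 1,461 = 12.5% of the window. This is the only measure of the gap that the documents support, and it is a share of calendar time, not of patients.

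**3. What it could mean in patients (illustration only).** At the pre-pandemic rate, half a year is 0.5 × 90,000 = 45,000. The documents do not say what fraction of that volume occurred in 2020, so a range is assumed:

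| Assumed fraction of 45,000 | Added | Total | Increase over 319,600 |
|---|---|---|---|
| 10% | 4,500 | 324,100 | 1.4% |
| 25% | 11,250 | 330,850 | 3.5% |
| 50% | 22,500 | 342,100 | 7.0% |
| 100% | 45,000 | 364,600 | 14.1% |

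The last row is probably an upper bound, since SAP 4.4.4 expects a small cohort.

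**4. The precision of the stated figure.** Every input is given as approximate. If 90,000 is rounded to the nearest 10,000 (an assumption), the error is up to 5,000 × 3.5 = 17,500 either way, and 17,500 / 319,600 = 5.5%. Since 17,500 / 45,000 = 38.9%, an omitted cohort below about 39% of the half-year volume lies within the tolerance the figure already carries. Data opt-outs (protocol 9.3) will move the final count as well.

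**5. What uses the total.** Neither document contains a target effect, a power or a precision requirement. Stopping rules are declared not applicable (protocol 11.6). Entry is set by the dated criteria. The analyses in SAP 5.4 compare the COVID-19 cohort with each comparator cohort separately, so no model takes the grand total as an input. The primary comparator in protocol 11.4 is pneumonia admitted up to 1 July 2019, which lies outside the uncounted half-year; SAP 4.4 does not rank its comparators, so this last point rests on the protocol.

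**The case for a change.** The best case for a correction has four parts.

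First, the sum is called a total and no sentence states the exclusion. That stands. It is softened because the sentence carrying the total, in both SAP 2.2 and protocol 11.3, names its two components, so a reader who compares it with the eligibility dates can see what is not counted. Only the synopsis is bare.

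Second, small is not quantified. Even 10% of the half-year volume is 4,500, about the size of the COVID-19 group of 4,600 that the plan itemises. With one-to-one matching, the size of this cohort matters for its own comparison. That is fair, but it concerns that cohort's count and not the grand total. SAP 5.4.3 already provides for full matching, or for inverse probability weighting if too many COVID-19 patients are lost.

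Third, rounding can go either way, whereas an omission can only understate. This is true. The tolerance argument shows only that the shortfall may be no larger than the existing imprecision, not that it is absent.

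Fourth, the study links confidential records without individual consent, so the declared number of people has descriptive weight. That also stands. However, the criteria and the comparator list determine whose records are drawn, and both disclose this cohort openly in the protocol and the SAP.

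**Conclusion.** The omission is a fact, but it is editorial. The two documents describe one cohort more than their approximate headcount includes. The arithmetic itself is right; the mismatch is one of scope between the sample-size paragraph and the eligibility criteria.

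No change to the plan follows because nothing in the study would differ. The same patients would be extracted, the same cohorts compared, and the same hazard ratios and intervals reported, whether the figure read 319,600 or anything up to 364,600. A sentence stating the exclusion would only write down what the criteria already let a reader work out. Restating the total would need a count that the documents do not hold. The actual number in each cohort will be known at extraction, and SAP 5.1 already presents baseline characteristics for each cohort separately.

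The size is 12.5% of the eligible calendar window. In patients it cannot be derived from the documents: it runs from 1.4% to 14.1% of the stated total across assumed fractions of 10% to 100% of the pre-pandemic volume, with the lower values fitting the SAP's expectation better. The conclusion rests on the study size being set by availability and on no power or precision claim being attached to the total. Had either document used 319,600 to justify a detectable difference, the point would need correcting.
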